4.7 Poolability Analysis

It is expected that data will be poolable across trial sites, as all sites and Investigators will follow a common protocol with identical inclusion/exclusion criteria and defined objective efficacy parameters.

Treatment effect will be evaluated by the proportion of subjects achieving hemostasis at 7 minutes by site. Trial site will be tested as a covariate in a logistic regression model, with the primary endpoint measure as the outcome. An additional logistic regression model will be fit to test for a Treatment by site interaction effect. In the case that poolability across site is confirmed, as indicated by statistical significance at $\alpha > 0.15$, the assumption of homogeneity will be accepted. In the case that poolability across site is questionable, as indicated by statistical significance at $\alpha \leq 0.15$, the assumption of homogeneity will be rejected. An additional primary

efficacy analysis will be fit in order to ascertain the treatment effect after adjustment for site.

Additionally, it is expected that data will be poolable across therapeutic areas. Potential variability in time to hemostasis between therapeutic areas is mitigated by limiting the types of procedures and bleeding severities for which subjects can be enrolled into the investigation.

The proportion of subjects achieving hemostasis at 7 minutes will be summarized by therapeutic area. The difference in proportions and its associated 95% confidence interval will also be reported by therapeutic area. Therapeutic area will be tested as a covariate in a logistic regression model, with the primary endpoint measure as the outcome. To test for a differential treatment effect across therapeutic area a logistic regression model will be fit, testing for the interaction of treatment group by therapeutic area. In the case that poolability across a therapeutic area is questionable, as indicated by statistical significance of the interaction effect at alpha ≤ 0.15 , the estimated treatment difference and 95% confidence interval from the subgroup adjusted logistic regression model will be reported.

The reasons for any differences in outcome across site and/or therapeutic area will be investigated and reported. Poolability analyses will be conducted on the AT population.

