6.6.2 Primary Efficacy Hypothesis

The primary efficacy hypothesis for this clinical investigation is that the proportion of subjects achieving hemostasis of the treated bleeding site at 7 minutes in the overall PerClot group is non-inferior to the proportion of subjects achieving hemostasis at 7 minutes in the overall control group.

$$H_0: P_{\text{PerClot}} < P_{\text{Control}} - \delta$$
$$H_a: P_{\text{PerClot}} \geq P_{\text{Control}} - \delta$$

where P_{PerClot} is the proportion of PerClot subjects achieving hemostasis at 7 minutes, P_{Control} is the proportion of control subjects achieving hemostasis of the treated bleeding site at 7 minutes, and δ is the non-inferiority margin, with $\delta = 0.10$.

The primary efficacy endpoint measure will also be reported by therapeutic area (subgroup): open elective cardiac, general, or urological surgical procedures. The proportion of PerClot and control subjects achieving hemostasis at 7 minutes will be reported, along with the absolute difference between the groups. A poolability analysis will also be performed on the therapeutic area subgroups. See Section 6.6.12. There are no labeling claims being sought out for this subgroup analysis.

Additionally, the number of subjects in whom hemostasis is achieved at 7 minutes, but have a re-bleed during the 5 minute observation period following the 7 minute assessment will be summarized. A sensitivity analysis of the endpoint will be conducted where all subjects that achieved hemostasis at 7 minutes, but did not maintain it for the 5 minutes following the assessment or any time after the observation period, will be counted as ‘failures’ in the analysis.

For subgroups, with an overall enrollment of 324 subjects in the study in the treatment and control cohorts, it is expected that there will be data on approximately 108 subjects in each subgroup. At a minimum, the study will enroll 50 subjects within a specific therapeutic area subgroup. At a maximum there will be 224 subjects in a single subgroup. A minimum of 50 subjects in each subgroup would lead to approximately 25 treatment subjects per subgroup. For a success rate of 92% (23/25), the distance from the observed rate of 92% to the lower bound of the two-sided 95% confidence interval is 18.0%. This planned minimum subgroup size would provide a reasonable degree of statistical precision for estimation of the treatment performance within subgroups.

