6.6.12 Poolability Analyses

It is expected that data will be poolable across trial sites and therapeutic areas, as all sites and Investigators will follow a common protocol with identical inclusion/exclusion criteria and defined objective efficacy parameters. Additionally, it is expected that data will be poolable across therapeutic areas. Potential variability in time to hemostasis between therapeutic areas is mitigated by limiting the types of procedures and bleeding severities for which subjects can be enrolled into the investigation.

Treatment effect will be evaluated by the proportion of subjects achieving hemostasis at 7 minutes by site, and again by therapeutic area. Each of these measures will be tested as a covariate in a logistic regression model, with the primary endpoint measure as the outcome. Additional logistic regression models will be fit to test treatment by site and treatment by therapeutic area interaction effects.

In the case that poolability across site or therapeutic areas is confirmed, as indicated by statistical significance at alpha > 0.15, the assumption of homogeneity will be accepted.

In the case that poolability across site or therapeutic areas is questionable, as indicated by statistical significance at alpha \leq 0.15, the assumption of homogeneity will be rejected. An additional primary efficacy analysis will be fit in order to ascertain the treatment effect after adjustment for site or therapeutic area. The reasons for any differences in outcome across these measures will be investigated and reported.

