- Hemostasis maintenance;
- Total intraoperative estimated blood loss;
- Alternative means required to achieve hemostasis (where applicable);
- Units of blood transfused intraoperatively and postoperatively (where applicable);
- Incidence of reoperation;
- Total hospitalization time;
- The incidence of procedure complications; and
- The incidence of adverse events through final follow-up, including, but not limited to:
 - Adhesions or fibrosis;
 - Anaphylaxis;
 - Blockage of the bladder or ureteral lumen;
 - Blockage of the bypass system;
 - Cancer recurrence and/or progression;
 - Compromised attachment of prosthetic devices to bone or tissue;
 - Death;
 - Embolism;
 - Failure of deep or superficial wound healing;
 - Failure to obtain hemostasis;
 - Fever;

- Hemorrhage;
- Infection;
- Peri-operative hyperglycemia;
- Exacerbation of surgical procedure-associated adverse events;
- Swelling and compression of pressure-sensitive tissues and structures;
- Thromboembolism;
- Thrombosis; and
- Toxicity.

Any procedure complications/adverse events through final follow-up will be reported as per Common Terminology Criteria for Adverse Events (2009): CTCAE-2009.¹

2 Study Subjects

Three hundred and twenty four subjects across a maximum of 25 investigational sites undergoing open elective cardiac, general, or urological surgical procedures who meet the eligibility criteria will be intraoperatively randomized to receive either PerClot or the control hemostatic device. Subjects will be randomized on a 1:1 basis. Randomization will be stratified by therapeutic area and bleeding severity score within site. Each investigational site is expected to enroll approximately 13-40 subjects. All investigational sites will be located in the U.S. Follow-up will occur at hospital discharge and 6 weeks post-device application.

The expected duration of each subject's participation in this investigation can range from a minimum of 28 to 56 days, based on the visit windows presented in Table 1. For oncology subjects, an additional follow-up will occur at 24 months.

Table 1: Visit Windows for Evaluations

Visit Type	Timing
Preoperative	Within 1 month (30 days) before operative visit
Operative	Day 0
Postoperative	Within 24 hours postoperatively
Follow-Up: Discharge	Within 24 hours of hospital discharge or between 24 hours and 14 days postoperatively
Follow-Up: 6 weeks	28 - 56 days postoperatively
Follow-Up: 24 Months*	23-25 months (700-760 days) postoperatively

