4.2.1.1 Sample Size Justification

The sample size was calculated based on the following assumptions:

- One-sided alpha = 0.025;
- Minimum 80% power;
- Non-inferiority margin $\delta = 0.10$;
- Expected 7 minute hemostatic success rate in the PerClot group is 90%; and
- Expected 7 minute hemostatic success rate in the control group is 90%.
- Randomization allocation of 1:1

A sample size of 154 subjects in each group will provide approximately 80% power to reject the hypothesis of the inferiority of PerClot to the composite control by a 10% margin, using a one-sided 97.5% confidence interval (see Appendix A). As the primary endpoint data is collected intraoperatively, no adjustment is made for attrition; however, the sample size was increased to account for the possibility of up to 5% loss within either group due to technical failures (i.e., contraindications, misdiagnosis, or intraoperative death prior to treatment, etc.), and subjects not treated according to randomization assignment, resulting in a sample size of 162 per arm to ensure >80% power. Thus, a total of 324 subjects is the planned sample size to enroll, assuming an efficacy rate of 90%.

A non-inferiority margin of 10% is consistent with the margins used in other controlled clinical trials involving hemostatic agents.^{2, 3} A non-inferiority margin $\delta = 0.10$ was chosen for this study because excluding a 10% difference between the treatments would be supportive of non-inferior performance of PerClot compared to the control.

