4.2.1.2 Blinded Sample Size Re-estimation

In order to protect against lower than planned power due to misspecification of the assumed success rates, blinded sample size re-estimation (BSSR) will be performed⁴. The initial sample size calculation will be repeated based on the observed pooled efficacy rate (i.e. the proportion of all subjects, regardless of randomization assignment, with 7 minute hemostatic success) rather than the initially assumed rate of 90%.

The re-estimation will be performed using the pooled efficacy results of the first 20% and 50% of the minimum planned enrollment of 324 (i.e. 64 and 162 subjects). The re-estimated sample size after 20% enrollment will provide an initial re-calibration of the sample size. The re-estimated sample size after 50% enrollment will determine the final sample size, which may

be lower or higher than the re-estimated sample size after 20% enrollment.

The sample size calculation will result in an increase in sample size if the observed efficacy rate is less than 90%. The loss rate at the interim analysis will be estimated and provided to the DSMB. In making a sample size recommendation, the DSMB may adjust the re-estimated sample size by up to 5% for the loss rate. The minimum sample size for the trial, regardless of the observed efficacy and loss rates, is the initially planned sample size of 324. A maximum sample size is set at 536 (510 with a 5% loss adjustment) for any observed efficacy rate $\leq 80\%$. The table below provides examples of the revised sample size before adjusting for loss based on hypothetical results.

Table 2: Re-estimated sample size based on blinded efficacy rate before adjusting for loss

Blinded Efficacy Rate	Re-estimated Sample Size
90%	308
89%	332
88%	352
87%	374
86%	394
85%	414
84%	434
83%	454
82%	474
81%	492
80%	510

Because the sample size re-estimation is blinded and based only on a nuisance parameter, there is no impact on the Type I error rate. Larger sample sizes are required due solely to greater variability in the binomial outcome when the equal PerClot and control efficacy rates are closer to 50%, at which point variability is at a maximum.

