4.2.3 Trial Success Criteria

Trial success will be the rejection of the primary efficacy null hypothesis, with the upper bound of the 97.5% one-sided confidence interval for the difference in proportions of subjects achieving hemostasis at 7 minutes between treatment groups ($P_{Control} - P_{PerClot}$) being less than 0.10, in the As Treated population.

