4.4.2 Primary Efficacy

Primary efficacy will be measured by the proportion of subjects achieving hemostasis of the treated bleeding site at 7 minutes. The hemostasis status at 7 minutes will be used to define this endpoint. If a subject achieves hemostasis at an earlier time assessment (i.e., 5 minutes), but begins to re-bleed and the bleeding has not ceased by the 7 minute assessment, the subject will not be counted as achieving hemostasis at 7 minutes. The proportion of subjects achieving hemostasis will be summarized by treatment group. The difference between groups will be reported, along with the 95% confidence interval of the difference. Non-inferiority will be evaluated by comparing the upper bound of the confidence interval for the difference in treatment proportions ($P_{Control} - P_{PerClot}$) to the non-inferiority margin of 0.10. If the upper bound is found to be less than 0.1, the null hypothesis will be rejected and treatment will be considered non-inferior to control.

This analysis will be performed on the AT, ITT, and PP populations. The AT population will serve as the primary analysis population for the evaluation of the primary efficacy endpoint. Analyses based on the ITT and PP populations will be presented as supportive analyses. Additionally, the number of subjects in whom hemostasis is achieved at 7 minutes, but have a re-bleed during the 5 minute observation period following the 7 minute assessment will be summarized. A sensitivity analysis of the endpoint will be conducted where all subjects that achieved hemostasis at 7 minutes, but did not maintain it for the 5 minutes following the assessment or any time after the observation period, will be counted as 'failures' in the analysis.

Of note is that only subjects who have achieved hemostasis at 7 minutes will be observed for the additional 5 minutes. In cases where the wound has not achieved hemostasis at 7 minutes, it would be considered a failure and the surgeon is instructed to treat using alternate methods. Likewise, if the subject achieved hemostasis at 7 minutes and there is a breakthrough or re-bleeding at any point between the 7 and 12 minutes of assessment or any time after the observation period, the surgeon will immediately treat with alternate methods.

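### With about 90% success and 13-40 subjects per site, the logistic treatment-by-site check does not operate at its stated 0.15 level: a Wald test almost never rejects, and a likelihood-ratio test rejects about twice too often at 8-12 sites

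*SAP*

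**What the plan says.** SAP 4.7 fits site as a covariate in a logistic model for 7-minute hemostasis and then adds an interaction: "An additional logistic regression model will be fit to test for a Treatment by site interaction effect". Protocol 6.6.12 has the same plan: "Additional logistic regression models will be fit to test treatment by site and treatment by therapeutic area interaction effects". A p-value above 0.15 means homogeneity is accepted. A p-value at or below 0.15 means it is rejected and a site-adjusted efficacy analysis is added. Neither section says whether the p-value is Wald, likelihood-ratio or exact, or what happens when a site-arm has no failures. SAP 4.6 mentions Type III p-values, but only for the covariate models.

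SAP section 2 allows at most 25 sites and states: "Each investigational site is expected to enroll approximately 13-40 subjects". SAP 4.2.1.1 assumes 90% success in both arms. Re-estimation may raise the total: "A maximum sample size is set at 536 (510 with a 5% loss adjustment").

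On the success rule, SAP 4.2.3 says "Trial success will be the rejection of the primary efficacy null hypothesis, with the upper bound of the 97.5% one-sided confidence interval" and SAP 4.4.2 says "The difference between groups will be reported, along with the 95% confidence interval of the difference". Neither names an interval method. SAP 4.2.1.1 gives a pointer: "using a one-sided 97.5% confidence interval (see Appendix A"). Appendix A uses the Farrington-Manning score test.

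**The concern.** A logistic interaction test over many sites relies on a chi-square approximation that needs several successes and several failures in each site-arm. At 90% success, a site-arm of 6 to 19 subjects is expected to have only 0.6 to 1.9 failures. Where an arm has none, that site's log odds ratio is infinite. Its Wald contribution falls to zero while its degree of freedom is still counted. The likelihood-ratio statistic remains finite, but its chi-square reference is poor.

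The 0.15 threshold then does not mean what it says. Programmed one way, the check can hardly ever find sites different. Programmed the other way, at 8-12 sites, it finds them different about twice as often as intended when they are not. The same data could support either conclusion, depending on a choice the plan leaves open.

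**Working it through.** **Plan's own figures first.** The Farrington-Manning formula at 154 per arm, 90% vs 90%, margin 0.10 and one-sided 0.025 gives power 0.79885, exactly as in Appendix A. It also reproduces SAP Table 2, from 308 (using 0.901, as in Appendix B) to 510. The sizing is therefore not in question.

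**Number of sites.** 324/40 = 8.1 and 324/13 = 24.9, so about 8 to 25. At 510 analysed, 510/40 = 12.8, so about 13 up to the cap of 25.

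**Sparse cells.** With K equal sites, N analysed and success rate p, each site-arm has m = N/(2K) subjects. The chance of at least one site-arm without failures is 1 - (1 - p^m)^(2K).
- N = 308, p = 0.90, K = 8: m = 19.25, 0.9^19.25 = 0.132, and 1 - 0.868^16 = 90% (89% by simulation).
- K = 12: m = 12.8, 0.9^12.8 = 0.259, giving 99.9%.
- K = 25: m = 6.2, 0.9^6.2 = 0.52, giving 100%.
- N = 510, p = 0.80: 28% at 13 sites (m = 19.6) and 99.6% at 25 sites (m = 10.2).

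**Rejection rates at nominal 15%.** Likelihood ratio (LR): saturated against site-plus-arm logistic model, K-1 df. Wald: inverse-variance chi-square on site log odds ratios, K-1 df, separated sites contributing zero. Both statistics were checked against a standard GLM fit on three datasets (LR identical, Wald within 0.02). Sites are equal in size, with 20,000 trials per row.

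| No true interaction | LR | Wald |
|---|---|---|
| 90%, 308, 8 sites | 28-29% | under 0.1% |
| 90%, 308, 12 sites | 31-32% | 0% |
| 90%, 308, 25 sites | 14-15% | 0% |
| 85%, 414, 12 / 25 sites | 28% / 42% | 0.3% / 0% |
| 80%, 510, 13 / 25 sites | 22-23% / 40% | about 4% / 0% |

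A separate run at N = 324 gave LR 27.7-32.5% and Wald at most 0.08% at 8-12 sites, and LR 16.7% at 25 sites. Twelve unequal sites of 13-40 gave LR about 28% and Wald 0%.

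The near-nominal LR rate at 25 sites is two errors offsetting. With 13 per site, only about 25 x (1 - 0.9^13) = 18.7 sites contain any failure, yet 24 df are charged. Charging df only for those sites gives about 62% rejection.

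**When sites do differ (assumed pattern).** Control is 90%, and PerClot alternates 98% and 72% by site. At 8 / 12 / 25 sites, Wald rejects about 1.5% / 0% / 0% and LR 89% / 83% / 52-53%. With a milder 97%/79% alternation, Wald rejects about 0.6% / 0% / 0%.

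**Replacements, 90% success, 8 / 12 / 25 sites.**
- Zelen's exact test: size 15.5% / 14.8% / 13.4%; power under 98/72 of 86% / 79% / 61%.
- Treatment permuted within site, risk-difference heterogeneity: size 15.3% / 14.8% / 15.1% with no treatment effect; power 88% / 79-80% / 62-66%. With a common difference of -10 points, size is 13.8% / 13.1% / 13.2%. Other settings gave 11-13% (95% vs 85%) and 9-11% (90% vs 70%).

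**Interval clarification.** By exact enumeration at 154 per arm and 80% vs 90%, one-sided alpha is 2.47% by score and 2.78% by Wald. Example: PerClot 137/154, control 142/154, difference 5/154 = 0.0325. The Wald standard error is sqrt(0.8896 x 0.1104/154 + 0.9221 x 0.0779/154) = 0.0332, so the upper bound is 0.0325 + 1.96 x 0.0332 = 0.098 (pass). The score bound is 0.101 (fail).

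**The case against.** The strongest reply is that little depends on this check. SAP 4.2.3 rests success on the overall bound in the As Treated population. SAP 4.7 evaluates hemostasis by site whatever the p-value, and has any differences investigated and reported. A missed interaction would not hide the site results, and a false alarm costs one extra analysis. That stands and limits the weight of the point. It does not make an acceptance of homogeneity informative when the test can hardly reject.

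It is also fair that the documents give no site-size distribution, that the heterogeneity patterns are assumed, and that the plan does not say Wald would be used. The level failure under homogeneity does not depend on the assumed patterns.

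Four stronger readings are tempting but not supported:
- **LR is inflated everywhere in the 13-40 range.** It is not: at 90% success and 25 sites it is about 14-17%.
- **The therapeutic-area test fails in the same way.** Protocol 6.6.2 allows small groups: "At a minimum, the study will enroll 50 subjects within a specific therapeutic area subgroup". At the extreme 50/50/224 split, LR rejects 21% and Wald 4.6%. The plan expects about 108 per area, where the chance of a no-failure cell is only 1 - (1 - 0.9^54)^6 = 2%.
- **The primary verdict is undefined because no interval is named.** SAP 4.2.1.1 points to Appendix A's score test, and Appendix B simulates the final test; exact score results match the fixed-design figures in SAP Table 3. No section proposes Wald.
- **Only the score test supports Table 3's type I error statement.** At Table 3's null (79.9% vs 90%), fixed 154 per arm, Farrington-Manning gives 2.33%, Miettinen-Nurminen 2.22% and Newcombe 2.41%. Of the four methods checked, only Wald, at 2.62%, exceeds 2.5%.

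**Conclusion.** The point holds for the treatment-by-site check. At about 90% success and 13-40 subjects per site, neither ordinary reading of the rule delivers a 0.15 test across the planned range. Wald is at about 0% throughout; LR is at about 28-32% for 8-12 sites and near nominal at 25. If success is 80% and 510 are analysed, LR is about 22% (13 sites) to 40% (25 sites), and Wald about 4% to 0%.

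These sizes assume a common success rate across sites, 1:1 allocation within site, mostly equal site sizes and K-1 degrees of freedom. The consequence is confined to the homogeneity conclusion and the trigger for the site-adjusted analysis; trial success is untouched. This should be corrected but does not threaten the primary result. The unnamed interval is a minor clarification only.

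**What to change.** 1. **SAP 4.7 and protocol 6.6.12, treatment by site.** Keep the 0.15 threshold and replace the large-sample interaction p-value with Zelen's exact test of equal odds ratios across sites. This keeps the odds-ratio scale of the current model. The alternative is to permute treatment within site, using the sum of squared deviations of site risk differences from their weighted mean, with weights n1 x n0/(n1 + n0). If that is chosen, state that homogeneity is now judged on the risk-difference scale and that size is approximate when there is a common non-zero effect.
2. **Site main effect.** Report it descriptively, or permute site labels within arm. Permuting treatment within site cannot test it.
3. **Minor wording.** In SAP 4.2.3, 4.4.2, 4.4.3 and protocol 6.6.7, name the Farrington-Manning score bound already implied by SAP 4.2.1.1 and Appendices A and B.

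The cost is a short program and SAP and protocol wording, with the protocol text going through the approvals in protocol 6.8 as applicable. Enrolment, margin, re-estimation and the sized primary test do not change.
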